### **3.2 Rationale of study design**

This study can be considered exploratory in nature as there are no published data describing the efficacy of switching treatment from aflibercept to ranibizumab in patients with nAMD where either no treatment response has been achieved or where there is suboptimal treatment response. It is recognized that there are potential patient and Investigator derived sources of bias in this study due to the unmasked design, but these are acceptable bearing in mind the exploratory nature of the study. A parallel group design to include either a sham injection group or continued injection of aflibercept cannot be justified at this stage as the patient population most likely to benefit from a switch from aflibercept to ranibizumab is unknown and there are insufficient data to assist in the development of sample size calculations that allow robust statistical conclusions to be achieved on potential between group differences.

The design of the study also reflects current clinical practice where patients who achieve suboptimal treatment responses with one anti-VEGF therapy will be switched to an alternative anti-VEGF therapy. The 6 month duration of the study is also reflective of the timeframe used in clinical practice to assess whether patients are likely to achieve a meaningful clinical response to an anti-VEGF therapy.

### **3.3 Rationale of dose/regimen, route of administration and duration of treatment**

In this study, ranibizumab will be administered at the SmPC and other product labels approved dose of 0.5mg and the dosing regimen is consistent with current clinical practice where re-treatment decisions are based not only on changes in VA but also on retinal morphology changes that may be indicative of disease activity (Myolonas 2009). Historical data from a number of clinical trials demonstrate that 0.5mg ranibizumab offers a favorable benefit-risk profile. Ranibizumab is administered as an IVT injection to maximize the bioavailability of the drug at the site of pathology while minimizing systemic exposure.

The posology section of the SmPC for ranibizumab recommends monthly injections until maximum visual acuity is achieved with additional injections thereafter in the event of a loss of visual acuity due to nAMD. In this study, this re-treatment criterion will be applied although in addition re-treatment will occur based on measures of increasing or persistent retinal disease activity as these are commonly used in clinical practice. The permitted interval between ranibizumab injections will be 23 to 37 days during the Monthly Treatment period and 23 days or greater during the PRN Treatment period. This study design is in keeping with the posology used in other prospective studies with ranibizumab in nAMD.

### **3.4 Rationale for choice of comparator**

No comparator will be used in this study.

### **3.5 Purpose and timing of interim analyses/design adaptations**

An interim analysis will be conducted after the first 50 patients complete the 90 day study visit. The primary objective for this analysis is to provide preliminary safety data in the proposed population of patients with nAMD. The secondary objective is to provide preliminary efficacy data.

### **3.6 Risks and benefits**

The risk to subjects in this trial will be minimized by compliance with the eligibility criteria and study procedures and close clinical monitoring. The management and monitoring of patients in this study reflects both the recommendations within the IB, SmPC, other international product labelling, and current clinical practice; there are no clinically relevant disadvantages from participating in this study. The risks associated with use of ranibizumab are well described in the IB, product labelling and patient information leaflet.

Patients who provide informed consent and enter this study, are currently not achieving optimal treatment response with aflibercept. The potential benefit to participants is that disease activity may be stabilized or improved with ranibizumab.

## **4 Population**

The study will include patients diagnosed with visual impairment due to nAMD who have been treated with aflibercept and where either no treatment response has been achieved or where there is suboptimal treatment response. Assuming an approximate 20% screen failure rate, approximately 155 patients will need to be screened to have 124 eligible patients commencing treatment in the trial. Approximately 40 ophthalmology centers in Western European countries will be initiated.

It is anticipated that patients with primary treatment failure to aflibercept (see Section 4.1 for definition) are likely to achieve small responses to treatment with ranibizumab. In order to minimize potential risks to these patients, a maximum of 30 patients will be recruited in this subgroup.

### **4.1 Inclusion criteria**

Patients eligible for inclusion in this study have to fulfill all of the following criteria:

#### **Inclusion criteria for patient**

1. Written informed consent must be obtained before any assessment is performed.
2. Age  $\geq 50$  years.
3. BCVA  $\geq 23$  ETDRS letters, at both the Screening Visit and Baseline Visit in the Study eye.
4. Active, angiographically documented CNV lesion in study eye (e.g. leakage on fluorescein angiography plus intraretinal, subretinal or sub-retinal pigment epithelium (RPE) fluid on SD/HD-OCT) secondary to AMD at Screening.

5. Evidence of active CNV involving the center of the fovea in the study eye (e.g. pigment epithelium detachment, subretinal or sub-RPE hemorrhage, macular edema, or subretinal, sub-RPE or intraretinal fluid) at Baseline.
6. The total area of fibrosis in the study eye comprising less than 50% of the lesion area.

### **Patient subgroup specific inclusion criteria**

Patients need to meet all the criteria for one of the following two groups:

#### Group 1. Primary treatment failure

7. No prior anti-VEGF treatment prior to initiating aflibercept.
8. Received no more than 3 injections of aflibercept into the study eye prior to the Screening Visit.
9. Historical OCT volume scan acquired  $\leq 28$  days before the first aflibercept injection was administered to the study eye.
10. Initiated treatment with aflibercept  $< 130$  days prior to the Screening Visit.
11. Last injection of aflibercept was  $\geq 28$  days but  $\leq 40$  days prior to the Baseline visit.
12. No increase in BCVA ( $\geq 5$  letters) since commencing treatment with aflibercept.
13. Disease activity has never been controlled in the study eye after initiating aflibercept as defined by at least one of the following observed on a historical OCT volume scan acquired after a minimum of 2 aflibercept injections: evidence of unchanged or increasing retinal\* or sub-retinal fluid; new PED; unchanged or increasing size of pre-existing PED.

#### Group 2. Suboptimal treatment response

14. No prior anti-VEGF treatment prior to initiating aflibercept.
15. Aflibercept commenced  $\geq 6$  months prior to the Screening Visit.
16. Received  $\geq 3$  aflibercept injections into the study eye within 6 months of the Screening Visit.
17. Historical OCT volume scan acquired  $\leq 28$  days before the first aflibercept injection was administered to the study eye.
18. Evidence of previous reduced disease activity in the study eye after initiating aflibercept as defined by reduction of  $\geq 50\mu\text{m}$  in central subfield retinal thickness observed on a historical OCT volume scan acquired after a minimum of 2 aflibercept injections.
19. Last injection of aflibercept was  $\geq 28$  days but  $\leq 70$  days prior to the Baseline visit.
20. At Screening Visit, disease activity has worsened (as defined by increasing retinal\* or sub-retinal fluid, or new or increasing size of PED) in the study eye compared to prior visits.

---

\* Evidence of increasing retinal fluid may include increased number, size or total volume of IRCs, or increased central retinal or foveal thickness, or similar quantitative retinal imaging data recorded within the individual patient record

## **4.2 Exclusion criteria**

Patients fulfilling any of the following criteria are not eligible for inclusion in this study. No additional exclusions may be applied by the Investigator, in order to ensure that the study population will be representative of all eligible patients.

### **Exclusion criteria for patient**

1. Inability to comply with study or follow-up procedures.
2. Pregnant or nursing (lactating) women, where pregnancy is defined as the state of a female after conception and until the termination of gestation, confirmed by a positive hCG laboratory test.
3. Women of child-bearing potential, defined as all women physiologically capable of becoming pregnant, unless they are using effective methods of contraception during dosing of study treatment. Effective contraception methods include:
  - Total abstinence (when this is in line with the preferred and usual lifestyle of the subject). Periodic abstinence (e.g., calendar, ovulation, symptothermal, post-ovulation methods) and withdrawal are not acceptable methods of contraception.
  - Female sterilization (have had surgical bilateral oophorectomy with or without hysterectomy) or tubal ligation at least six weeks before taking study treatment. In case of oophorectomy alone, only when the reproductive status of the woman has been confirmed by follow up hormone level assessment.
  - Male sterilization (at least 6 months prior to screening). For female subjects in the study, the vasectomized male partner should be the sole partner for that subject.
  - Barrier methods of contraception: Condom or Occlusive cap (diaphragm or cervical/vault caps) with spermicidal foam/gel/film/cream/vaginal suppository.
  - Use of oral, injected or implanted hormonal methods of contraception or other forms of hormonal contraception that have comparable efficacy (failure rate <1%), for example hormone vaginal ring or transdermal hormone contraception.
  - Placement of an intrauterine device (IUD) or intrauterine system (IUS).

In case of use of oral contraception women should have been stable on the same pill for a minimum of 3 months before taking study treatment.

Women are considered post-menopausal and not of child bearing potential if they have had 12 months of natural (spontaneous) amenorrhea with an appropriate clinical profile (e.g. age appropriate, history of vasomotor symptoms) or have had surgical bilateral oophorectomy (with or without hysterectomy) or tubal ligation at least six weeks ago. In the case of oophorectomy alone, only when the reproductive status of the woman has been confirmed by follow up hormone level assessment is she considered not of child bearing potential.

**Exclusion criteria for systemic medical history and conditions**

4. History of cerebrovascular accident, transient ischemic attack or myocardial infarction within 3 months of the Screening visit.
5. Any type of systemic disease or its treatment, including any medical condition (controlled or uncontrolled) that could be expected to progress, recur, or change to such an extent that it may bias the assessment of the clinical status of the patient to a significant degree or put the patient at special risk.
6. Uncontrolled blood pressure defined as a persistent systolic value of >160 mm Hg or persistent diastolic value of >100 mm Hg at Screening or Baseline.
7. Simultaneous participation in any other clinical study for the duration of this study.
8. Use of other investigational drugs (excluding vitamins and minerals) or participation in any other clinical study within 90 days or 5 half-lives of the Screening visit, or until the expected pharmacodynamic effect has resolved, whichever is longer.
9. History of hypersensitivity to either ranibizumab (or any component of the ranibizumab formulation), or fluorescein, or indocyanine green, or to drugs of similar chemical classes.

**Exclusion criteria for ocular medical history and conditions**

**For either eye**

10. Any active periocular or ocular infection or inflammation (e.g., blepharitis, conjunctivitis, keratitis, scleritis, uveitis, endophthalmitis) at the time of Screening or Baseline.
11. Uncontrolled glaucoma (intraocular pressure [IOP]  $\geq 30$  mm Hg on medication or according to Investigator's judgment) at the time of Screening or Baseline.
12. Evidence of bilateral active CNV during the Screening Period or at Baseline requiring bilateral anti-VEGF injections. Patients with active CNV in the study eye with quiescent CNV in the fellow eye who may have received IVT aflibercept or ranibizumab injections into the fellow eye >40 days prior to the Screening visit are not excluded from the study; however, should the fellow eye require anti-VEGF treatment during the study only ranibizumab may be utilized.
13. Prior intravitreal injection of ranibizumab or bevacizumab into the study eye and/or prior intravitreal injection of bevacizumab into the fellow eye

**Study eye exclusion criteria**

14. At Baseline, intraocular surgery was performed within the previous 28 days or intraocular surgery is planned at any time during the 6 month study period.
15. Cataract (if causing significant visual impairment), aphakia, severe vitreous hemorrhage, rhegmatogenous retinal detachment, proliferative retinopathy or choroidal neovascularization of any other cause for CNV other than wet AMD (e.g., ocular histoplasmosis, pathologic myopia ( $\geq -6$  dioptries)) at the time of Screening and Baseline.
16. Irreversible structural damage involving the center of the fovea (e.g. advanced fibrosis or geographic atrophy) which in the opinion of the Investigator is sufficient to irreversibly impair visual acuity.

17. Polypoidal choroidal vasculopathy (PCV), RPE tear, central serous retinopathy (CSR), or significant vitreomacular traction identified during Screening period or within 4 months of Baseline visit. Note that small vitreomacular adhesions that do not result in deformity of the retina are permitted.
18. Any other ocular abnormality unrelated to AMD that is in the Investigator's opinion is likely to contribute to progressive deterioration in visual acuity over the next 6 months.
19. Prior laser therapy or use of verteporfin photodynamic therapy.
20. Prior use of intra- or peri-ocular corticosteroids within 6 months of Screening.
21. Unable to obtain at Screening SD/HD-OCT images of sufficient quality to be analyzed.

## **5 Treatment**

### **5.1 Protocol requested treatment**

#### **5.1.1 Investigational treatment**

The investigational treatment/study drug in this study is ranibizumab 0.5mg (Lucentis®).

Ranibizumab solution for injection will be supplied in either pre-filled syringes (PFS) or vials according to local availability. Each PFS or vial contains ranibizumab in a concentration of 10mg/ml (labeled as RFB002 0.5mg/0.05ml, corresponding to a 0.5mg dose).

Study medication will be supplied in commercially available packaging. Each vial or PFS will be labeled with the appropriate information. Medication labels will comply with the legal requirements and be printed in the local language. The storage conditions will be described on the label.

Ranibizumab is formulated as a sterile solution aseptically filled in a sterile glass vial or PFS. Each vial/PFS contains ranibizumab in an aqueous solution (pH 5.5) with histidine, trehalose and polysorbate 20. The vial/PFS contains no preservatives. It is suitable for single use only and the content of the vial/PFS must not be split. Ranibizumab must be stored according to label instructions and it must be kept in a secure locked facility.

#### **5.1.2 Additional study treatment**

No additional treatment beyond investigational treatment is requested for this trial.

### **5.2 Treatment arms**

All eligible patients will be assigned to active treatment with ranibizumab.

### **5.3 Treatment assignment, randomization**

This is not a randomized study. Patients will meet eligibility criteria for either the primary treatment failure subgroup or the secondary suboptimal response subgroup (see Section 4.1). Recruitment of patients into the primary treatment failure subgroup will be up to a maximum of 30 patients. Recruitment to this subgroup will be closed once this number of patients has been allocated to the primary treatment failure subgroup, and have both successfully completed the Screening assessments and confirmation of eligibility has been entered into the eCRF.

At the Baseline Visit (Day 1), all eligible patients will receive IVT injection of ranibizumab 0.5mg into the study eye. Repeat ranibizumab injections will only occur at scheduled study visits; i.e. at Day 30 ( $\pm 7$ ) and Day 60 ( $\pm 7$ ). Repeated ranibizumab injections may also occur according to the protocol defined re-treatment criteria (see Section 5.5.4) at Day 90 ( $\pm 7$ ) and Day 120 ( $\pm 7$ ). After each visit has been performed the eCRF needs to be updated with the details of whether an injection has been administered or not.

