### **PRN treatment period: Day 61 to Day 180**

Efficacy and safety assessments will be repeated (see Table 6-1) at Day 90, 120, 150 and 180. All subjects will attend Scheduled Study Visits every 30 ( $\pm 7$ ) days. The primary endpoint will be evaluated when patients have completed assessments at the Day 90 visit.

Between the Day 90 and Day 150 visits inclusive, the decision to administer ranibizumab 0.5mg will be at the discretion of the Investigator and driven either by persistent or worsening visual symptoms attributed by the Investigator to nAMD, or worsening visual acuity ( $>1$  letter decline since last Study Visit) or by the presence of persistent or worsening disease activity on OCT\*. Source documentation must provide evidence for one or more of these retreatment criteria. Injections of IVT ranibizumab to the study eye, where required, should occur on the same day as the scheduled study visit.

Final efficacy and safety assessments will be conducted at Day 180.

---

\* Persistent or worsening disease activity on OCT includes the presence of sub-retinal fluid, persistent or increased number, size or total volume of IRCs, or increased central retinal or foveal thickness, or similar quantitative retinal imaging data recorded within the individual patient record.

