#### **5.5.4.2 PRN Treatment Period: Day 90 to Day 180**

All patients will have monthly assessments of BCVA and disease activity assessed by OCT. These assessments, together with an assessment of the patient's visual symptoms, will be used for the decision of potential re-treatment with ranibizumab. This PRN regimen, will permit re-treatment with ranibizumab at Day 90, Day 120 and/or Day 150 if in the opinion of the Investigator persistent or worsening visual symptoms are attributed to nAMD, and/or if there is evidence of worsening ETDRS best corrected visual acuity (>1 letter decline since last Study Visit) and/or the presence of persistent or worsening disease activity on OCT\*. Source documentation must provide evidence for one or more of these retreatment criteria.

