#### **5.5.4.3 Treatment of the Fellow Eye**

Patients who develop visual impairment due to nAMD in the fellow eye (non-study eye) during the study that, in the Investigator's opinion, qualifies for and requires treatment, may be treated at the Investigator's discretion according to the standard of care, including ocular administration with ranibizumab. This eye is then called the fellow treated eye.

Ranibizumab will be provided by the Sponsor (supplied for investigational treatment) and should be administered according to the SmPC or local labelling. Details of all PFS and vials administered will be recorded on drug accountability forms and a record of the administration also included in the eCRF.

Treatment of the fellow eye must be scheduled in a way not to disturb the schedule for visits and treatments of the study eye. Ideally injection of the fellow eye should occur on the same day as a scheduled study visit in order to minimize the total number of clinic visits required by the patient. Bilateral IVT injections of ranibizumab may occur at any scheduled study visit between Day 30 and Day 150. The fellow treated eye must be monitored according to routine practice and AE(s) and SAE(s) must be captured in the eCRF. Should injection of the fellow eye occur at a visit other than a scheduled study visit, this should be recorded in the eCRF as an unscheduled study visit and all protocol specified procedures for an unscheduled visit should be completed (see Section 6).

If in the Investigator's opinion, the fellow eye requires further treatment with ranibizumab, this should not occur more frequently than monthly in accordance with the posology section of the SmPC. A protocol deviation will be recorded should the patient receive a repeat ranibizumab injection into the fellow eye less than 23 days after the previous injection into the fellow eye. However, the patient will not be withdrawn from the study.

At the time when treatment of the fellow eye is being initiated, the BCVA assessment for the fellow eye should be repeated and recorded in the eCRF.

Treatment with other anti-VEGF medication other than ranibizumab is prohibited in either eye at any time during the study.

---

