**Table 6-2 Assessment schedule (peri-injection procedures, safety assessments and venous blood sample collection)**

	Screening V1	Baseline V2	V3	V4	PEV V5	V6	V7	EOS or EWW V8	UNSCHED V
Dispense topical antibiotic medication according to local practice		(X)	(X)	(X)	(X)	(X)	(X)		
Ranibizumab injection		X	X	X	(X)	(X)	(X)		
Post-injection assessments		X	X	X	(X)	(X)	(X)		
Vital signs	X	X	X	X	X	X	X	X	X
Height and Weight	X								
Adverse events	X	X	X	X	X	X	X	X	X
PEV: Primary Endpoint Visit. EOS: End of Study visit also incorporates the Early Withdrawal Visit (EWW). UNSCHED V: Unscheduled visit (X) Indicates that local standard practice should be applied or in the case of ranibizumab injection, that Investigator judgment is used to determine whether repeat injection is required.									

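### Protocol section 5.3 names Day 90 and Day 120 as the PRN injection visits and omits Day 150, which four other places in the protocol include

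*Protocol*

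**What the plan says.** Protocol section 5.3 first limits repeat dosing to planned visits ("Repeat ranibizumab injections will only occur at scheduled study visits") and specifies Day 30 and Day 60. It then turns to the PRN period: "Repeated ranibizumab injections may also occur according to the protocol defined re-treatment criteria". The same sentence goes on to the days: "see Section 5.5.4) at Day 90 ( $\pm 7$ ) and Day 120 ( $\pm 7". The list ends there, and Day 150 is not in it.

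Four other places include Day 150:

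- Section 3.1, PRN treatment period: "Between the Day 90 and Day 150 visits inclusive, the decision to administer ranibizumab 0.5mg will be at the discretion of the Investigator".
- Section 5.5.4.2: the PRN regimen "will permit re-treatment with ranibizumab at Day 90, Day 120 and/or Day 150".
- Section 5.5.4.3, on the fellow eye: "Bilateral IVT injections of ranibizumab may occur at any scheduled study visit between Day 30 and Day 150". A bilateral injection at Day 150 presupposes that the study eye can be injected then.
- Table 6-2 marks the ranibizumab injection with a bracketed X at V5, V6 and V7. Its footnote explains that, "in the case of ranibizumab injection, that Investigator judgment is used to determine whether repeat injection is required". Table 6-1 dates V7 as Day 150±7.

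Section 5.5.5 does not allow the PRN regimen to be adjusted, and gives sections 3.1 and 5.5.4 as the places where that regimen is described. It does not mention section 5.3.

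**The concern.** The difference is in operative treatment text, so it is more than clerical. It decides whether the last PRN visit can carry an injection. A site that withholds at Day 150 and a site that injects at Day 150 could each point to current protocol wording.

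Four things depend on the answer:

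- **Exposure.** SAP section 2.1.7 reports injections in total and by visit. A low count at Day 150 could reflect inactive disease or a reading of section 5.3.
- **PRN compliance.** SAP section 2.1.7 divides injections given by injections required under the re-treatment criteria.
- **Discontinuation status.** Protocol section 5.5.9 requires study treatment to stop when two sequential injections that were due were withheld or missed. Whether a Day 150 injection was due depends on which list applies.
- **Day 180 secondary outcomes.** The changes in CSRT and BCVA to Day 180, and in BCVA from Day 90 to Day 180, are read at a different distance from the last possible injection under the two lists.

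**Working it through.** The documents state no figure that could be reproduced. The check is a side-by-side reading followed by simple counts.

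**Visits at which the study eye may be injected**

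| Place in protocol | Fixed injections | PRN injections |
|---|---|---|
| Section 5.3 | Day 1, 30, 60 | Day 90, 120 |
| Section 3.1 | Day 1, 30, 60 | Day 90 to 150 inclusive |
| Sections 5.5.4.1 and 5.5.4.2 | Day 1, 30, 60 | Day 90, 120, 150 |
| Table 6-2 with Table 6-1 | V2, V3, V4 (Day 1, 30, 60) | V5, V6, V7 (Day 90, 120, 150) |
| Section 5.5.4.3 | not listed | bilateral injection possible up to Day 150 |

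The fixed injections agree everywhere. Only the last PRN visit differs.

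**Maximum study-eye injections** (fixed + PRN)

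- Section 5.3: 3 + 2 = 5.
- The other places: 3 + 3 = 6.

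**Nominal interval from the last possible injection to the Day 180 assessment**

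- Section 5.3: 180 − 120 = 60 days.
- The other places: 180 − 150 = 30 days.

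**PRN compliance, illustration only.** Take a patient who meets the criteria at all three PRN visits, is injected at Day 90 and Day 120, and is not injected at Day 150 because the site followed section 5.3. The SAP formula gives 100 × 2/3 = 66.7%. This is a worst case for a single patient, not an estimate for the trial.

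**Two-missed rule, illustration.** Take a patient whose due injection at Day 120 was withheld, who meets the criteria at Day 150 and is not injected. If Day 150 is a permitted visit, two sequential injections were missed and the rule in section 5.5.9 applies. If it is not, only one was missed. Table 6-2 marks no injection at V8, so what changes is mainly the patient's recorded discontinuation status, not later dosing of the study eye.

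**Primary endpoint.** The primary variable is the CSRT change to Day 90. Protocol section 6.4 requires efficacy assessments to precede the injection at each visit. No PRN injection, at Day 150 or earlier, can therefore affect a Day 90 measurement taken as planned, and the sample size depends on no PRN visit.

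**The case against.** The strongest reply is that section 5.3 omits Day 150 without prohibiting it. Its sentence is permissive and sends the reader to section 5.5.4. The word that restricts dosing in the preceding sentence governs scheduled visits, and Day 150 is a scheduled visit. That sentence's own list of Day 30 and Day 60 is not exhaustive either, since the next sentence adds visits. Section 5.3 also concerns assignment in a single-arm study without randomisation, while section 5.5.5 names sections 3.1 and 5.5.4 as describing the PRN regimen. Those two sections agree with each other and with the visit table.

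Most of this stands. It makes divergent practice less likely, and it rules out treating the two lists as rival schedules of equal standing. It does not remove the discrepancy. Section 5.5.5 forbids adjusting the regimen but does not say that one section prevails over another, and a reader who meets a list of named days may reasonably take it as complete.

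Two further objections stand in full:

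- The SAP's PRN compliance denominator is driven by the re-treatment criteria and names no visit days, so it contains no list that conflicts.
- The deviation definitions are in the protocol deviation module that SAP Appendix 2 refers to. Its content is not in the available documents, so nothing shows that a Day 150 injection, or its absence, would be miscoded.

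**Conclusion.** The discrepancy is real and is in current text: 2 against 3 PRN decision points, at most 5 against 6 study-eye injections, and a nominal 60 against 30 days between the last possible injection and Day 180. It should be corrected, but its expected effect is modest. Section 5.3 is a single outlying sentence, and how often a site would act on it is unknown and cannot be derived from the documents.

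Three stronger readings are tempting and are not supported:

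- A reader might infer that up to 124 patients would be treated inconsistently. That would require every site to follow section 5.3 over the regimen sections and the visit table.
- A reader might take 67% as a likely compliance figure. It needs a patient who meets the criteria at all three PRN visits and goes without the Day 150 injection solely because of section 5.3.
- A reader might suppose that the main result is at risk. The Day 90 primary endpoint and the sample size are untouched, and the visible text plans only descriptive summaries for the Day 180 secondary outcomes (SAP section 2.2.2.2).

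What could be affected is exposure by visit, PRN compliance, the two-missed-injections rule and the interpretation of the Day 180 summaries. This assumes that at least some Day 150 decisions were made on the wording of section 5.3.

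**What to change.** Reconcile section 5.3 with section 3.1, sections 5.5.4.2 and 5.5.4.3, and Tables 6-1 and 6-2, so that one list of PRN injection visits applies throughout. Which list is right is for the sponsor to decide. The simplest form is either to state the agreed visits in section 5.3 or to have it refer to section 5.5.4 without naming days.

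Leave the SAP compliance formula as it is. Once the list is settled, check the deviation coding in the SAP's protocol deviation module against it.

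The cost is about one sentence in the next amendment or a clarification letter, plus the coding check before database lock.
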